Specific Aim: H1-2. This analysis focuses on assessing the effect of lithium on: (H1) cognitive performance and, (H2) neuroimaging measures of hippocampal volumes and total gray matter and cognition. Outcomes are measured at three time points, and our primary analysis will consist of linear mixed effects models. These models will include a term for time, group and a time-by-group interaction. We will test for lithium effect by testing the significance of the coefficient associated with the interaction term in the model as well as by a likelihood ratio test between the models with and without interaction. First, we will fit these basic models for each of the outcomes of interest and test for the time-by-group interaction as an assessment of the effect of lithium. Second, we will include potential covariates (e.g., age, education, sex, etc.) and exploratory covariates (e.g., physical activity) that may influence the group effect and test for a time-by-group interaction in this context. We will examine the biomarker trajectories across the two groups. If the assays used to measure the biomarkers produce results outside of the detectable limits, we will use tobit model and mixed model extensions of the tobit model to test for differences between the two groups.

POWER ANALYSIS. For H1a/H2a, where 80 subjects will be randomized to one of two groups with 64 completers (32 in each cell), we computed power based on the following assumptions: a two-sided significance level of 0.05, a power of 0.80 and measurements at three time points for a repeated measures model. Based on these assumptions, we are powered to observe an effect size (Cohen's **d**) of 0.57 (i.e., medium) when the observations are correlated at a level of 0.5 across time. The effect size ranges from 0.45 to 0.60, a little over a half standard deviation difference in the outcome variable, as the correlation between repeated observations ranges from 0.1 to 0.6. We also computed the effect size for a two-sided significance level of 0.01, a more conservative alpha for testing multiple outcomes, and power of 0.80 as above and found that the effect size ranged from 0.54 to 0.72 as the correlation between repeated observations ranged from 0.1 to 0.6.

References

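### The covariate step names no covariate-by-time terms, so read literally it leaves the lithium slope contrast unadjusted for fixed baseline covariates

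*Combined protocol and SAP*

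**What the plan says.** Under Statistical Considerations, the paragraph on Specific Aim H1-2 sets up linear mixed models with terms for time, group and their interaction, fitted to three measurement times. The treatment test is stated directly: "We will test for lithium effect by testing the significance of the coefficient associated with the interaction term in the model", together with a likelihood ratio test of the same term.

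That basic model is fitted first for each outcome. The next step reads "Second, we will include potential covariates (e.g., age, education, sex, etc" and goes on to "exploratory covariates (e.g., physical activity) that may influence the group effect and test for a time-by-group interaction in this context". Three things are left open:

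- whether covariates enter as main effects only or also with time;
- whether physical activity is a baseline value or a repeated measure;
- which covariates are finally used, since both lists are given by example.

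Study Design & Methods says that randomisation is stratified on baseline amyloid PET. That factor is not among the covariates named.

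**The concern.** The lithium effect in this plan is a difference in rates of change. To adjust it for age, say, the model must let the rate of change depend on age. Adding age as a main effect lets only the level depend on age. The paragraph spells out the time-by-group term but for covariates says only that they are included, so a programmer following the text would most naturally fit main effects.

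The result would then be reported as covariate-adjusted although, for age, education and sex, it neither corrects chance imbalance in predictors of decline nor gains precision. In a trial with 32 completers per arm that serves as the go/no-go for a larger study, a reader could take agreement between the two steps as evidence that imbalance does not matter, when the second step had not examined it.

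**Working it through.** **The plan's own figure.** The POWER ANALYSIS paragraph has "80 subjects will be randomized to one of two groups with 64 completers (32 in each cell" and a detectable d "of 0.57 (i.e., medium) when the observations are correlated at a level of 0.5 across time". For a difference averaged over m = 3 visits with n = 32 per arm,

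d = (1.960 + 0.842) × sqrt(2(1 + 2ρ)/(3 × 32)).

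At ρ = 0.5 this is 2.802 × sqrt(4/96) = 0.572, so the stated 0.57 reproduces. At ρ = 0.1 and 0.6 it gives 0.443 and 0.600, against the stated 0.45 and 0.60. No covariate enters this calculation, so the power statement does not depend on the second step. (The formula is for a time-averaged difference, not the time-by-group test; that is a separate matter.)

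**Why a main effect cancels.** Take time as linear (the plan speaks of one coefficient), with visits at 0, 1 and 2 years. With complete data, each participant's fitted slope is (y₂ − y₀)/2, and the time-by-group estimate is the difference in mean slope between arms. A baseline covariate x with main effect β adds βx to both y₂ and y₀, so it drops out. If x also predicts rate of change, with coefficient γ per year, each slope contains γx and the contrast contains γ × (difference in mean x between arms). Only an x-by-time term removes that part.

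**Simulation.** 100 trials per scenario, 40 per arm, random-intercept REML fits. Assumptions, none from the documents: within-participant correlation about 0.5; age changes the slope by −0.25 SD per year per SD of age; dropout, where present, depends on age.

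| Data | Added to basic model | Mean absolute change in time-by-group | Mean SE, basic → new |
|---|---|---|---|
| Complete | age, education, sex main effects | 0.00000 | 0.1172 → 0.1172 |
| About 20% dropout | same main effects | 0.011 (max 0.040) | 0.1282 → 0.1280 |
| Complete | same, each with time | 0.052 (max 0.187) | 0.1172 → 0.1135 |
| About 20% dropout | same, each with time | 0.057 (max 0.190) | 0.1282 → 0.1245 |

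With dropout, main effects move the estimate by 0.011/0.128 = 0.09 SE on average. The covariate-by-time terms move it by 0.057/0.128 = 0.44 SE. A separate generalised least squares check with random intercepts and slopes, correlated −0.5, 0 or 0.5, also gave no change with complete data, so the result does not depend on the random-effects structure.

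**Physical activity.** Suppose activity is recorded at each visit, falls by 0.5 SD per year more on lithium, and is worth 0.3 SD of outcome per SD (all assumed). Its main effect alone should then move the contrast by 0.5 × 0.3 = 0.15 per year. The simulation gave 0.150, with the estimate going from −0.142 to 0.008.

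**Net precision of the adjusted model.** For k covariates and N completers, the SE ratio for a contrast of change is about sqrt((1 − R²)(N − 3)/(N − 3 − k)), where R² is the share of the variance of change that they explain. With N = 64 and k = 4 the second factor is 61/57 = 1.070.

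| R² (assumed) | SE ratio | Change in SE |
|---|---|---|
| 0 | sqrt(1.070) = 1.034 | about +3% |
| 0.05 | sqrt(0.95 × 1.070) = 1.008 | about neutral |
| 0.10 | sqrt(0.90 × 1.070) = 0.981 | about −2% |
| 0.20 | sqrt(0.80 × 1.070) = 0.925 | about −8% |

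A simulation of change scores with four covariates and 64 completers gave the same pattern.

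**The case against.** The strongest reply is that the plan does not say main effects only. It is silent, and covariates chosen because they may influence the group effect, itself defined as time-by-group, could be meant to enter with time. That stands: the documents do not support saying that the plan prescribes a wrong model. They support saying that the model form is unspecified and that its plain reading does not adjust the contrast.

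A second reply is that the primary inference is untouched. That also stands. A reader might infer that the lithium test is biased, but randomisation keeps the basic contrast unbiased and its SE already reflects chance imbalance.

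Third, a reader might infer that the basic and adjusted results must agree. That holds for fixed baseline covariates with complete data, and closely on average with dropout. It does not hold for physical activity measured after randomisation, which could move the contrast by more than one SE (0.150 against about 0.12 in the assumed scenario). That shift would come from conditioning on a variable that lithium may affect, so it is not a correction for baseline imbalance.

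Finally, the precision at stake is easily overstated. Taking sqrt(1 − R²) alone suggests SE reductions of 5% and 11% at R² of 0.10 and 0.20, but this ignores the cost of estimating the covariate terms. The documents give no R², and with weak covariates the adjusted model could be slightly less precise.

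**Conclusion.** The point holds as a minor defect confined to the second step. Followed literally, that step leaves the time-by-group coefficient exactly unchanged with complete data for age, education and sex, and changes it by under one tenth of an SE on average with about 20% dropout (about 0.3 SE in the most affected simulated trial, 0.040/0.128). It therefore does not do what an adjusted analysis is for. The complete-data result is algebraic and needs no assumed effect size. The dropout figures rest on the assumed correlation, age-by-time slope and dropout pattern, and the precision figures on assumed R². The result does not extend to covariates that vary over time, and nothing here calls the basic test into question.

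**What to change.** State in the SAP that the adjusted model contains a short prespecified list of baseline covariates, first the amyloid PET stratum used in randomisation and then age, education and sex. Each should enter as a main effect and with its covariate-by-time term, and the adjusted time-by-group coefficient should be taken from that model. State also that physical activity, if used, enters only as its baseline value.

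This is a change of SAP wording. The amyloid scan is already a baseline procedure for all participants. The statistical cost is one further degree of freedom per single-parameter covariate, and a slightly larger SE if the covariates predict little of the change. Both argue for closing the open-ended list and keeping it short.

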Specific Aim: To examine the potential disease modifying properties of lithium in individuals with MCI in delaying conversion to dementia.

H1: a) Participants randomized to take lithium for two years, compared to placebo, will better maintain cognitive function, primarily in memory, which b) will be associated with changes in biomarkers (e.g., GSK-3 β activity, BDNF).

H2: a) Participants randomized to take lithium for two years, compared to placebo, will have larger hippocampal volumes and lower total gray matter thinning, which b) will be associated with changes in biomarkers (e.g., GSK-3 β activity, BDNF) and c) better cognitive function, primarily in memory.

Exploratory Aim: To examine whether lithium is related to additional markers of enhanced brain integrity (e.g., lower level of microbleeds, higher white matter integrity, better network connectivity, or decreased CSF phospho tau levels).

Study Design & Methods

Enroll and randomly assign 80 individuals 60 years and older with MCI to take lithium, titrated as tolerated to a blood level of 0.6 to 0.8 mEq/L, or placebo for two years to assess lithium's effects on preserving cognition and delaying conversion to dementia. Participants will receive annual neurocognitive assessment, ultra-high field (7T) brain MRI (e.g., high-resolution imaging of hippocampal and total cortical gray volumes, white matter integrity, dynamic imaging), blood- (e.g., GSK-3 β , BDNF, cytokines) and CSF-based (e.g., A β , total tau, and phospho tau) biomarker measurement. All subjects will undergo baseline PET imaging of A β on which to stratify randomization. *This study is powered to detect medium/large effect sizes for H1-2, and will serve as the “go/no-go” for a subsequent, larger-scale, confirmatory study.*

Eligibility Criteria

Inclusion criteria:

1. 60 years or older
2. Diagnosis of Mild Cognitive Impairment

Exclusion criteria:

1. Major psychiatric illness (mild psychiatric illness may be included)
2. Major neurologic illness (e.g., multiple sclerosis)
3. Contraindication to lithium (e.g., renal insufficiency)
4. Unable to complete neuropsychological testing due to non-remediable impairment (e.g., blindness)

Statistical Considerations

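### The stated power fits a group difference averaged over three visits, not the time-by-group interaction that tests lithium; if d = 0.57 is a two-year difference in change, power at correlation 0.5 is about 63%, not 80%

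*Combined protocol and SAP*

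**What the plan says.** Under Statistical Considerations, the Specific Aim: H1-2 paragraph specifies linear mixed models with terms for time, group and their interaction, on outcomes measured at three time points. It is explicit about the test: "We will test for lithium effect by testing the significance of the coefficient associated with the interaction term in the model", together with a likelihood ratio test of the models with and without the interaction.

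The Power Analysis paragraph that follows covers H1a/H2a. It takes 80 randomized and 64 completers, 32 per arm, and assumes "a two-sided significance level of 0.05, a power of 0.80 and measurements at three time points for a repeated measures model". It reports a detectable Cohen's d of 0.57 at correlation 0.5. For between-visit correlations of 0.1 to 0.6 it adds (quoted in part): "The effect size ranges from 0.45 to 0.60, a little over a half standard deviation difference in the outcome variable, as the correlation between". At two-sided 0.01 the authors "found that the effect size ranged from 0.54 to 0.72 as the correlation between repeated observations ranged from 0.1 to 0.6". The paragraph does not say which contrast was powered, or that d is a difference in change or slope.

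Study Design & Methods relies on these figures: "This study is powered to detect medium/large effect sizes for H1-2". It also makes the trial the go/no-go for a larger confirmatory study.

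**The concern.** The stated detectable effect grows as the correlation between visits grows. That is how a between-person average behaves: the more alike a person's visits are, the less each extra visit adds. An interaction is a within-person contrast. Higher correlation removes more noise from it, so its detectable effect in outcome SDs should shrink. The pattern suggests that the power was worked out for a different contrast from the one to be tested.

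The go/no-go decision has no numeric threshold in the documents, so the power statement is the only advance guide to what a null result would rule out. It implies a 20% chance of missing d = 0.57. If d is a difference in two-year change, that chance is about 37% at correlation 0.5.

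**Working it through.** **Inputs from the plan.** n = 32 completers per arm; three visits; power 0.80; two-sided alpha 0.05 or 0.01; correlations r = 0.1 to 0.6; d in SDs of the outcome (SD = 1). Visits are taken at years 0, 1 and 2, from the annual assessments over two years in Study Design & Methods.

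**Assumptions not in the plan.** Compound symmetry (one common correlation), linear time, completers only.

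**Step 1: reproduce the plan's figures.** For a group difference in the three-visit mean,

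d = (z_alpha/2 + z_power) × sqrt[(2/32)(1 + 2r)/3],

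where the z sum is 2.802 at alpha 0.05 and 3.417 at alpha 0.01. At r = 0.5 this is 2.802 × sqrt(0.0625 × 0.6667) = 0.572.

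| alpha | r | Plan | Visit average |
|---|---|---|---|
| 0.05 | 0.1 | 0.45 | 0.443 |
| 0.05 | 0.5 | 0.57 | 0.572 |
| 0.05 | 0.6 | 0.60 | 0.600 |
| 0.01 | 0.1 | 0.54 | 0.540 |
| 0.01 | 0.6 | 0.72 | 0.732 |

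All five agree to about 0.01. A t-based version (62 df) gives 0.450, 0.581 and 0.609, then 0.555 and 0.752, so neither version is exact. Alternatives fit worse. At alpha 0.05, over r = 0.1 to 0.6, the mean of the two post-baseline visits gives 0.52 to 0.63, and the baseline-adjusted final visit falls from 0.70 to 0.56.

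**Step 2: the planned test.** With three equally spaced visits and compound symmetry, the linear slope contrast equals last visit minus first, with variance 2(1 − r) per person. The standard error of the between-arm difference in two-year change is therefore

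SE = sqrt[(2/32) × 2(1 − r)] = 2 × sqrt[(1 − r)/32],

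which is 0.335, 0.250 and 0.224 at r = 0.1, 0.5 and 0.6. Multiplying by the z sum gives the effect detectable with 80% power:

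| r | alpha 0.05 | alpha 0.01 |
|---|---|---|
| 0.1 | 0.94 | 1.15 |
| 0.5 | 0.70 | 0.85 |
| 0.6 | 0.63 | 0.76 |

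These fall with r, whereas the plan's figures rise. Expressed in SDs of the two-year change, the detectable effect is 0.70 at every r. Read as an annual slope, it falls from 0.47 to 0.31. No interaction reading examined gives a range that rises from 0.45 to 0.60.

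**Step 3: power of the interaction at the plan's effects, with d as the difference in two-year change.** At r = 0.5, 0.57/0.250 = 2.28; 2.28 − 1.96 = 0.32; power is 62.6%.

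| alpha | r | d | Power |
|---|---|---|---|
| 0.05 | 0.1 | 0.45 | 27% |
| 0.05 | 0.5 | 0.57 | 63% |
| 0.05 | 0.6 | 0.60 | 77% |
| 0.01 | 0.1 | 0.54 | 17% |
| 0.01 | 0.6 | 0.72 | 74% |

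Holding d at 0.57 and alpha at 0.05, power runs from 40% at r = 0.1 to 72% at r = 0.6. If all 40 per arm contribute fully, power at d = 0.57 and r = 0.5 is 72%. Simulation of the three alpha 0.05 pairs gave 26.7%, 61.9% and 75.8%.

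**Step 4: other readings of d at r = 0.5.**
- The same difference at all three visits, baseline included: interaction power equals alpha, 5%.
- A three-visit average of 0.57 with arms equal at baseline: the year-2 difference must be 0.57 × 3/2 = 0.86 SD (constant after baseline) or 0.57 × 2 = 1.14 SD (linear divergence). Interaction power is then 93% or over 99%.

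**Step 5: where the two contrasts break even.** Setting 4(1 − r) = (2/3)(1 + 2r) gives r = 0.625. Above that, outside the plan's range, the interaction does better than the stated figures.

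**The case against.** The strongest reply is that the 63% mixes two meanings of d. If the figures come from a visit average, d should be carried through as one. With arms equal at baseline, as randomization leads one to expect, a three-visit average of 0.57 implies a year-2 difference of 0.86 to 1.14 SD, and interaction power at correlation 0.5 is 93% or more. On that reading there is no shortfall at the plan's central case; power falls short only at low correlation (52% to 77% for d = 0.45 at 0.1). This arithmetic is right, which is why the 63% is conditional. But it supports the plan only by requiring a year-2 effect of 0.86 SD or more, well above the 0.57 that the plan calls medium.

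Three further points stand in part. The visit-average formula is inferred from the match, since the document names no formula. Linear time is an assumption: a 2-df interaction test with categorical time and linear divergence has about 51–52% power at d = 0.57 and correlation 0.5, and random slopes would also change the figures. And the gap is small at correlation 0.6 (0.63 against 0.60 SD), while the documents give no correlation for any outcome.

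It is also fair that a null result should be read mainly from the interaction estimate and its standard error. That does not make the advance power claim correct.

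**Conclusion.** The concern holds. The 80% power is not shown for the planned test: the figures closely match a visit-averaged difference, and their rise with correlation does not fit an interaction on any scale examined. The direction of that trend does not depend on how the effect is scaled, though it does rest on compound symmetry.

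The size of the error depends on what d means, which the plan leaves undefined. Read as a between-arm difference in two-year change in outcome SDs, the interaction at correlation 0.5 has about 63% power for 0.57 and needs 0.70 SD for 80%. This also assumes 32 completers per arm, linear time and two-sided 0.05. The shortfall is largest at correlation 0.1 and slight at 0.6. What is established is that the stated power belongs to another contrast; whether real power is too low depends on the outcome's correlation and the effect expected.

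**What to change.** Define the effect size for the interaction contrast, state whether time is linear or categorical and what random effects are fitted, and replace the detectable effects. If time is linear, the following would serve:

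> With 32 completers per arm and 80% power, the time-by-group interaction detects a between-arm difference in baseline-to-year-2 change of 0.70 cross-sectional SD at a correlation of 0.5 (0.94 at 0.1, 0.63 at 0.6) at two-sided 0.05, and 0.85 SD (1.15 to 0.76) at 0.01, assuming linear time and compound symmetry.

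If time is categorical or random slopes are fitted, recompute on that basis. Then check the power claim in Study Design & Methods against the new figures: 0.63 to 0.70 SD still fits its medium/large wording, but 0.94 SD at correlation 0.1 goes beyond it.

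The cost is wording only: N = 80 and the analysis are unchanged. The downside is a less favourable detectable effect across the plan's correlation range. For comparison, keeping 80% power for 0.57 SD of two-year change at correlation 0.5 would take 49 completers per arm, or 98/0.8, about 123 randomized at the implied 20% loss. That enlargement is not proposed here.
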